1 CLINICAL STUDY PROTOCOL SYNOPSIS

Name of Company	
Mitsubishi Tanabe Pharma Corporation	
Name of Investigational Product	
Oral Edaravone	
Name of Active Ingredient	
Edaravone (3-methyl-1-phenyl-2-pyrazolin-5-one)	
Study Protocol	MT-1186-A-301
Title of Study	A Phase 3, Multicenter, Open-label Extension Study following the studies MT-1186-A03 or A04 to Evaluate the Safety of Oral Edaravone in Subjects with Amyotrophic Lateral Sclerosis (ALS)
Study Centers	Multi-center study
Study Period	Planned date of first subject enrolled: October 2022 Planned date last subject completed: August 2023 (This study will be changed from a clinical study to a post marketing study after oral edaravone is approved by the regulatory authority in Japan.)
Phase	3 This study will be continued as a post marketing study since the date of approval by the regulatory authority in Japan in order to provide the subjects with the opportunity of taking oral edaravone.

Name of Company Mitsubishi Tanabe Pharma Corporation	
Name of Investigational Product Oral Edaravone	
Name of Active Ingredient Edaravone (3-methyl-1-phenyl-2-pyrazolin-5-one)	
Objectives	
Primary Objective:
 
 • To evaluate the long-term safety of oral edaravone at a dose of 105 mg administered once daily for 10 days out of a 14-day period, followed by a 14-day drug-free period. This study will be continued until the earlier date when oral edaravone is commercially available at each site or August 31st, 2023. 
Exploratory Objective:
 
 • To evaluate the efficacy of oral edaravone at a dose of 105 mg administered once daily for 10 days out of a 14-day period, followed by a 14-day drug-free period. This study will be continued until the earlier date when oral edaravone is commercially available at each site or August 31st, 2023. 
The subjects will be provided with the opportunity of taking oral edaravone by participating in this study.

Methodology	
This is a Phase 3, multi-center, open label extension study following the studies MT-1186-A03 or 04 to evaluate the long-term safety of oral edaravone. In this study, the subjects will take oral edaravone at a dose of 105 mg administered once daily for 10 days out of a 14-day period, followed by a 14-day drug-free period.
 
Eligible subjects who will complete Week 96 of MT-1186-A03 study or Week 48 of MT-1186-A04 study will be enrolled in this study. The subjects must continue to fast at least 1 to 2 hours post-dose before the next meal (eg, breakfast). The cycle of doses consists of 28 days, or a dose of 105 mg administered once daily for 10 days out of a 14-day period, followed by a 14-day drug-free period. Further details can be found in the Schedule of Activities (Table 1) and the Study Schema (Figure 1).

Planned Number of Subjects	Approximately 30 subjects, depending on how many subjects will complete Week 96 of Study MT-1186-A03 and Week 48 of MT-1186-A04, and will meet eligibility criteria in Study MT-1186-A-301.

Diagnosis and Main Inclusion Criteria and Exclusion Criteria	
Inclusion Criteria:
 
1 Subjects must provide a signed and dated informed consent form (ICF) to participate in the study.2 Subjects must be able (in the judgment of the Investigator) to understand the nature of the study and all risks involved with participation in the study.3 Subjects must be willing to cooperate and comply with all protocol restrictions and requirements.4 Subjects who successfully complete Week 96 of Study MT-1186-A03 or Week 48 of Study MT-1186-A04 and have been compliant with study drug (80-120%). 
Exclusion Criteria:
 
1 Subjects of childbearing potential who are not tested negative by a pregnancy test, subjects who are breastfeeding, and subjects who are unwilling to use a highly effective method of contraception from the Visit #1 until 3 months after the last dose of study medication. Refer to Attachment 2 for additional contraceptive information.2 Subjects who have a significant risk of suicide. Subjects with any suicidal behavior or suicidal ideation of type 4 (active suicidal ideation with some intent to act, without a specific plan) or type 5 (active suicidal ideation with specific plan and intent) based on the C-SSRS at Week 96 of the MT-1186-A03 study or at Week 48 of the MT-1186-A04 study.3 Subjects who are not eligible to participate in the study, as judged by the Investigator.4 Subjects who cannot receive drugs orally or via PEG/RIG.
---	---

[figure not shown]
Name of Company	
Mitsubishi Tanabe Pharma Corporation	
Name of Investigational Product	
Oral Edaravone	
Name of Active Ingredient	
Edaravone (3-methyl-1-phenyl-2-pyrazolin-5-one)	
Endpoints	
Primary Safety Endpoint: The safety of oral edaravone will be evaluated by the following safety assessments:
 
• AEs and adverse drug reactions• Physical examination;• Body weight;• 12-lead electrocardiogram (ECG) parameters;• Vital signs (heart rate, respiratory rate, sitting systolic and diastolic blood pressure, and axillary, oral or tympanic body temperature [method should be consistent throughout the study period]);• Orthostatic Vital Sign Measurement• Laboratory safety assessments (hematology, chemistry, urinalysis and pregnancy). 
Exploratory Efficacy Endpoints: The efficacy of oral edaravone will be evaluated by the following efficacy assessments:
 
• Score of ALS Functional Rating Scale-Revised (ALSFRS-R) at each visit• Events for death, tracheostomy or permanent assisted mechanical ventilation (≥ 23 hours/day) (If such events are found, the date of onset)

Statistical Methods	
Continuous variables will be summarized descriptively using the number of observations (n), mean, SD, median, minimum, and maximum. Categorical variables will be summarized using frequency counts and percentages.
 
Determination of Sample Size: The study sample size is not based on power and statistical considerations but on the number of eligible subjects who will complete Week 96 of MT-1186-A03 or Week 48 of MT-1186-A04. Approximately 30 subjects plan to be enrolled in this study.
 
Analysis Set: Statistical analyses will be conducted based on the following analysis set.
 
Safety Analysis Set: The Safety Analyses Set (SAF) is defined as all subjects who received at least 1 dose of study drug in Study MT-1186-A301.
 
Study Medication Exposure: The duration of exposure in days will be calculated as follows: “Date of last dose of edaravone in MT-1186-A301” – “Date of first dose of edaravone in MT-1186-A301” + 1 If the date of first dose or the date of the last dose cannot be determined, then the duration calculation will not be completed. The duration of exposure will be summarized using descriptive statistics. All exposure data will be listed. Interruptions and compliance are not taken into account for calculations of duration of exposure.
 
Analysis for Exploratory Efficacy Endpoints: The ALSFRS-R scores will be listed descriptively at each visit. The number and percentage of events for death, tracheostomy or permanent assisted mechanical ventilation (≥ 23 hours/day) will be listed at each visit.
 
Analysis for Safety Endpoints: TEAEs will be summarized using the number of subjects and percentage by system organ class (SOC) and preferred term (PT) and will be presented as follows:
 
• TEAEs by SOC and PT• TEAEs by SOC, PT, and severity• TEAEs by SOC, PT, and drug relationship• TEAEs leading to discontinuation of study drug by SOC and PT
----------------------------	---

Name of Company	Mitsubishi Tanabe Pharma Corporation
Name of Investigational Product	Oral Edaravone
Name of Active Ingredient	Edaravone (3-methyl-1-phenyl-2-pyrazolin-5-one)
	
• TEAEs leading to death by SOC and PT• TEADRs by SOC and PT• TEADRs by SOC, PT, and severity• Serious TEAEs by SOC and PT• Serious TEAEs related to study drug by SOC and PT 
Data collected from other safety evaluations will be summarized descriptively and/or listed according to the data type and will include the following:
 
• Body weight;• 12-lead ECG;• Vital signs (including orthostatic);• C-SSRS

Mitsubishi Tanabe Pharma Group

Protocol: MT-1186-A-301

Abbreviation: EOS = end-of-study, ET = early termination.

- a. Subjects will receive oral edaravone 105 mg once daily dosing for 10 days out of a 14-day period, followed by a 14 day drug free period. Oral edaravone will be administered following an overnight fast and subjects must continue to fast at least 1 to 2 hours post-dose before the next meal (e.g, breakfast).
- b. Evaluations for EOS will be performed at an earlier date of either “commercial oral edaravone available at each study site” or “August 31st,2023”. When commercial oral edaravone is available at each study site, the investigator should ask subjects to visit the study site and complete their EOS visit. If the EOS visit is completed prior to Week 24, no tests or evaluations for Week 24 will be done.
- c. When the treatment is discontinued prior to completion of the study, the investigator should complete the ET evaluations within seven days after the discontinuation.

Figure 1 : Study Schema

Table 1 : Schedule of Activities

Assessment	Week (window)	1 (x): Based on Week 96 of MT-1186-A03 or Week 48 of MT-1186-A04. No re-tests or evaluations will be performed for MT-1186-A-301 study	24 (± 7D)	EOS/ET ^a (± 7D)
Cycle	1	7		
Visit	1	2	3	
Informed consent	X			
Eligibility criteria	X			
Demographics ^b	X			
Vital signs ^c	(X)	X	X	
Orthostatic vital signs	(X)	X	X	
Pregnancy test (urine)	X	X	X	
Full Physical examination ^{d1}	(X)			X
Routine physical examination ^{d2}		X		
12-lead ECG ^e	(X)	X	X	
Body weight	(X)	X	X	
Event of death, tracheostomy or permanent assisted mechanical ventilation ^f	(X)	X	X	
Hematology ^g	(X)	X	X	
Chemistry ^h	(X)	X	X	
Urinalysis ⁱ	(X)	X	X	
Dispense edaravone ^j	X	X		
ALSFRS-R	(X)	X	X	
C-SSRS	(X)	X	X	
IMP compliance ^k	(X)	X	X	
Adverse events	(X)	X	X	

Abbreviation: D = Day; ECG = Electrocardiogram; C-SSRS = Columbia–Suicide Severity Rating Scale; ALSFRS-R = ALS functional rating scale- revised; EOS = End-of-study; ET = early termination.

- a. Subjects who withdraw from the study will complete the procedures listed in ET within 7 days of study discontinuation. In this case, the investigator should make maximum effort to check their conditions via phone.
- b. Demographics will include age, sex, race, and ethnicity.
- c. Vital signs will include sitting systolic and diastolic blood pressure, heart rate, respiratory rate, and axillary, oral or tympanic body temperature. The procedure should be the same throughout the study.
- d. Physical examination:
 - 1. A full physical examination will consist of an assessment of major body systems: abdominal, cardiovascular, general appearance, head, eyes, ears/nose/throat, lymph nodes, musculoskeletal, neck, neurological, dermatological, respiratory, and other.
 - 2. Routine physical examination will include an assessment of major body systems: abdominal, cardiovascular, general appearance, respiratory, neurological, and other.

Mitsubishi Tanabe Pharma Group

Protocol: MT-1186-A-301

- e. A 12-lead ECG will be performed after the subject has rested for at least 5 minutes in a supine position. The ECG must include the following measurements: R wave to R wave (RR) interval, heart rate, QRS, QT, QTcB, and QTcF. The Investigator will perform an overall evaluation of the ECG for safety purposes and the recording will be reported as ‘normal’, ‘abnormal clinically significant (CS)’, or ‘abnormal not clinically significant (NCS)’. Abnormalities of clinical significance will be reported as AEs.
- f. Events are death, tracheostomy, or permanent assisted mechanical ventilation (> 23 hours/day).
- g. To include: red blood cell count, hemoglobin, hematocrit value, white blood cell count, and platelet count.
- h. To include: albumin, total protein, aspartate aminotransferase (AST), alanine aminotransferase (ALT), Gamma glutamyl transferase (GGT), lactate dehydrogenase (LDH), alkaline phosphatase (ALP), total bilirubin, direct bilirubin, creatine kinase (CK), total cholesterol, triglycerides, blood urea nitrogen (BUN), bicarbonate, serum glucose, serum creatinine level, uric acid, sodium (Na), potassium (K), chloride, calcium (Ca).
- i. To include protein, glucose, occult blood, urobilinogen, white blood cells, and bilirubin.
- j. Subjects will receive oral edaravone 105 mg once daily dosing for 10 days out of a 14-day period, followed by a 14 day drug free period. Treatment cycles are every 4 weeks until an earlier date of either “commercial oral edaravone available at each study site” or “August 31st, 2023”, following an overnight fast and subjects must continue to fast at least 1 to 2 hours post-dose before the next meal (eg, breakfast).
- k. When subjects visit their study sites, IMP compliance will be evaluated at each cycle by study staff members.

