10.2 Vital Signs

The following measurements will be performed and be recorded in the eCRF: systolic and diastolic blood pressure, heart rate (e.g., beats per minute), respiratory rate, and axillary, oral, or tympanic body temperature (e.g., Celsius) and the same method is to be used throughout the study. Subjects must be in a supine position in a rested and calm state for at least 5 minutes before blood pressure assessments are conducted. If the subject is unable to be in the supine position, the subject should be in the most supine position as possible. The position selected for a subject should be the same that is used throughout the study and documented on the CRF.

The Investigator will perform an overall evaluation for safety purposes and the recording will be reported as 'normal', 'abnormal clinically significant (CS)', or 'abnormal not clinically significant (NCS)' and be recorded in the eCRF.

Abnormalities of clinical significance will be reported as AEs. Repeat measurements will be performed if needed.

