15.3 Statistical Analyses

15.3.1 General Considerations

The statistical analysis will be performed using SAS® Version 9.4 or higher.

Continuous variables will be summarized descriptively using the number of observations (n), mean, standard deviation (SD), median, minimum, and maximum. Categorical variables will be summarized using frequency counts and percentages.

All individual subject data will be listed.

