8.2.2 Vital signs

Absolute values will be summarized for the following parameters by analysis visit.

- Systolic blood pressure (mmHg)
- Diastolic blood pressure (mmHg)
- Heart rate (beats/min)
- Respiratory Rate (beats/min)
- Body temperature (°C)

For overall evaluation, number and percentage will be presented by analysis visit.

All data (including overall evaluation) will be listed.

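### Does the conflict between sitting and supine resting blood pressure call for a change to the vital-signs analysis?

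*Protocol*

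**What the plan says.** Resting blood pressure is described in several places, and they do not agree on posture.

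- **Protocol synopsis, primary safety endpoint:** the item is "sitting systolic and diastolic blood pressure".
- **Protocol Table 1, footnote c:** "Vital signs will include sitting systolic and diastolic blood pressure, heart rate, respiratory rate". The same footnote asks for one procedure to be kept throughout the study.
- **Protocol 10.2:** "Subjects must be in a supine position in a rested and calm state for at least 5 minutes before blood pressure assessments are conducted". It then allows for subjects who cannot lie flat: "If the subject is unable to be in the supine position, the subject should be in the most supine position as possible". It closes with a consistency and recording rule: "The position selected for a subject should be the same that is used throughout the study and documented on the CRF".
- **Protocol 5.2.1 (endpoints in the body of the protocol), SAP 2.1.1 and SAP 3.3 footnote c:** systolic and diastolic pressure, with no posture given.
- **SAP 8.2.2:** "Absolute values will be summarized for the following parameters by analysis visit". Posture is neither named nor used to split the summary. The section ends: "All data (including overall evaluation) will be listed".
- **Protocol 15.3.1:** "All individual subject data will be listed".

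Protocol 10.3 starts from a seated reading, but that is the separate orthostatic test, with its own schedule row and its own SAP section (8.2.3).

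**The concern.** A site working from the synopsis or Table 1 would seat the subject. A site working from 10.2 would have the subject lie down. Both could believe they were following the protocol. The one departure listed in SAP section 10 concerns another item, so the SAP does not settle the matter. The blood pressure table could therefore pool readings taken in different positions, and a reader who turned to the protocol for the missing label would find two answers. Because blood pressure is one of the primary safety assessments, this looks like an undefined measurement condition behind a primary result.

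**Working it through.** The plan gives no figure to reproduce. The check has two parts: a comparison of the passages, and an illustration of the largest distortion that mixing could cause.

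**1. Is the conflict real?** Yes. Sitting appears in the synopsis and in Table 1 footnote c, and supine in 10.2. The allowance in 10.2 applies only when a subject cannot lie supine, so supine remains its default. No other section decides between them.

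**2. What does the analysis do with the values?**

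- The sample size is not based on power (Protocol 15.1), and the study has one arm (12.5).
- SAP 8.2.2 plans absolute values only, with no change from baseline.
- The pre-defined limits in SAP 7.1.3.3 cover QTcF, heart rate and QRS on the ECG. None is a blood pressure limit.
- The abnormality criteria in Protocol 10.3 belong to the orthostatic test and its own seated baseline.
- The investigator's rating (normal, clinically significant, not clinically significant) and any resulting adverse event are judged subject by subject under 10.2, not from the pooled mean.
- SAP 7.2 restricts the analyses to EOS/ET, because no subject reached Week 24.

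**3. Can the posture be recovered?** Protocol 10.2 puts it on the CRF and fixes it within a subject. Protocol 15.3.1 and SAP 8.2.2 promise full listings. Neither names position as a field, but it falls naturally within them.

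**4. How large could the effect on the table be?** Every input here is an assumption except n = 30, which is the approximate planned enrolment. Let k subjects use the second posture, with p = k/30. Let d be the mean difference between postures and s the SD within a posture.

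Shift in the mean, relative to everyone in the first posture, is p × d:

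| k | p | d = 2 mmHg | d = 5 mmHg | d = 10 mmHg |
|---|---|---|---|---|
| 0 | 0 | 0 | 0 | 0 |
| 3 | 0.100 | 0.20 | 0.50 | 1.00 |
| 8 | 0.267 | 0.53 | 1.33 | 2.67 |
| 15 | 0.500 | 1.00 | 2.50 | 5.00 |

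Reported SD is √(s² + p(1 − p)d²). In the most extreme row (k = 15, d = 10), p(1 − p)d² = 0.25 × 100 = 25:

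- s = 10: √125 = 11.18, a rise of 11.8%; the shift is 5/10 = 0.50 SD.
- s = 15: √250 = 15.81, a rise of 5.4%; the shift is 5/15 = 0.33 SD.
- s = 20: √425 = 20.62, a rise of 3.1%; the shift is 5/20 = 0.25 SD.

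In a middle case (k = 8, d = 5, s = 15), the SD is √(225 + 4.89) = 15.16 and the mean moves by 1.33 mmHg.

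**5. Would one stated posture remove the mixing?** Not necessarily. Protocol 10.2 read alone already permits different positions between subjects, and the ALSFRS-R orthopnea item in Appendix 1 has a category for people who can sleep only when upright. Some mixing could occur in this population even with a perfectly consistent text.

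**The case for a change.** The strongest case for acting is that the contradiction is verbatim, concerns a primary safety item and is cheap to address. The field is already required on the CRF, so a split by position, or a count for each position, needs no new data. The rule in 10.2 prevents a change of posture within a subject but not a mixture between subjects. SAP 9.2 still names Day 1 among the visits to report. If Day 1 values are shown beside EOS/ET, readers will compare them informally, and the Day 1 readings come from the parent studies, whose posture these documents do not give.

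The text conflict stands, and so does the possibility of an unlabelled mixture, although the documents do not show that any mixing occurred. The step to a change in the plan does not stand. SAP 7.2 confines the analyses to EOS/ET, and no change from Day 1 is planned in any case. Both footnote c and 10.2 ask for consistency throughout. A split table would also be awkward, because a position described only as being as near supine as possible is not a clean category, and subgroups of a study with about 30 subjects would be small. Correcting the protocol now cannot affect readings already taken.

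**Conclusion.** The concern identifies a genuine drafting inconsistency but not a defect that requires the analysis plan to change. The synopsis, Table 1 footnote c and Protocol 10.2 do need to be reconciled as a matter of text, and this review takes no view on which posture is right. The consequence is at most a missing label on one descriptive table. Under the assumed inputs, the distortion of the mean runs from zero to 5 mmHg, and the upper end depends on an even 15/15 split together with a 10 mmHg difference. No comparison, threshold, investigator rating or adverse event report depends on that mean. A competent analyst would carry the recorded position into the listing and note the position or positions used in a footnote or in the study report.

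This conclusion rests on two things that the documents require but do not demonstrate: that position was in fact recorded on the CRF, and that it appears in the listings. If position was not recorded, the study report should say so. The analysis would be the same.

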Attachment

Attachment 1 Administrative Structure

Attachment 2 List of Study Sites and Investigators

3 LIST OF ABBREVIATIONS

Abbreviations	Unabbreviated expressions
AE	Adverse event(s)
AIS	Acute ischemic stroke
ALS	Amyotrophic lateral sclerosis
ALSFRS-R	ALS Functional Rating Scale-Revised
ALT	Alanine aminotransferase
AST	Aspartate aminotransferase
AUC	Area under the concentration-time curve
AUC _{0-24h}	Area under the concentration-time curve till 24 hours
AUC _{0-∞}	Area under the concentration-time curve till infinity
BCRP	Breast cancer resistant protein
C _{max}	Maximum concentration
CI	Confidence interval
CS	Clinically significant
C-SSRS	Columbia-Suicide Severity Rating Scale
CYP3A4	Cytochrome P450 3A4
DDI	Drug-drug interaction
ECG	Electrocardiogram
eCRF	Electronic case report form
EDC	Electronic data capture
EOS	End-of-study
ET	Early termination
FDA	Food and Drug Administration
GCP	Good Clinical Practice
GLP	Good Laboratory Practice
ICF	Informed consent form
ICH	International Conference on Harmonization
IRB	Institutional Review Board
IV	Intravenous
MedDRA	Medical Dictionary for Regulatory Activities
NCS	Not clinically significant
OAT3	Organic anion transporter 3
PEG	Percutaneous endoscopic gastrostomy

Abbreviations	Unabbreviated expressions
PK	Pharmacokinetic
PT	Preferred Term
RIG	Radiologically Inserted Gastrostomy
SAE	Serious adverse event
SAP	Statistical analysis plan
SOC	System organ class
SUSAR	Suspected unexpected serious adverse reactions
t_{max}	Time to maximum concentration
TEAE	Treatment-emergent adverse event(s)
ULN	Upper limit of normal
USPI	United States Package Insert
WMA	World Medical Association

4 INTRODUCTION

4.1 Background

Amyotrophic lateral sclerosis (ALS) is a rare disease that causes progressive and fatal neurodegenerative disorders.^{1,2} Currently, incurable, respiratory failure leads to death in a mean time of 2 to 4 years for the majority of ALS subjects, after the onset of the first symptoms. However, 5–10% of subjects may survive for a decade or more.³

Early stages of the disease appear in several forms and the lack of biological markers make ALS particularly difficult to diagnose. ALS is typically diagnosed by excluding other possible diseases. The El Escorial criteria have been developed and revised by the World Federation of Neurology;^{4,5} the criteria are based on clinical signs, electrophysiological and neuroimaging evidence, and allow for the diagnosis of ALS in 5 categories: definite ALS, probable ALS, probable laboratory-supported ALS, possible ALS, or suspected ALS.

ALS is a disease of unknown cause in which primary motor neurons (upper motor neurons) and secondary motor neurons (lower motor neurons) degenerate and are lost selectively and progressively. The symptoms are dominated by muscle atrophy and muscle weakness, with upper limb dysfunction, gait disturbance, dysarthria, dysphagia, and respiratory impairment appearing with the progression of illness, and with no sensory dysfunction or dysuria. As the mechanism of motor neuron death, excitatory amino acid hypothesis, free radical hypothesis, and viral infection hypothesis have been proposed.

Rilutek® (Riluzole) was first approved by the United States (US) Food and Drug Administration (FDA) in December 1995. Riluzole is indicated to extend life or the time to mechanical ventilation for subjects with ALS and represents the baseline standard of pharmacological care. Additional care is provided to reduce symptomatic medical concerns. Survival of ALS subjects has improved over time, mainly as a result of the improvement in the symptomatic care of ALS.^{6,7}

Edaravone (MCI-186), developed by Mitsubishi Tanabe Pharma Corporation, is a free radical scavenger which reduces oxidative stress and slows the progression of ALS as estimated by Amyotrophic Lateral Sclerosis Functional Rating Scale-Revised (ALSFRS-R). The clinical development program was designed to evaluate functional changes in ALS versus placebo up to 24 weeks. The concomitant use of riluzole was permitted in both edaravone and placebo groups in previous studies. Efficacy of edaravone has been demonstrated in definite or probable ALS subjects diagnosed with El Escorial criteria.^{8,9,10,11} Higher relative quality of life (QOL) has been demonstrated in subjects receiving edaravone as compared to the placebo group, and these differences were maintained up to 48 weeks.¹² Evidence regarding the delay of some of the definite disease progression events (including “death, disability of independent ambulation, loss of upper limb function, tracheotomy, use of respirator, use of tube feeding, and loss of useful speech”) was also found at 48 weeks.¹² During the edaravone clinical development program, all fatal events, which occurred after respiratory failure, pneumonia or cardiac arrest, or serious adverse events (SAEs), such as

gastrointestinal or respiratory disorders, were attributed or suspected to be attributed to the disease progression. However, higher incidence of contusion, gait disturbance, headache, eczema, contact dermatitis, and glucosuria was reported in the edaravone group.¹³ Most of the population of the clinical program development of edaravone was Japanese. However, a pharmacokinetic (PK) analysis compared Japanese and Caucasian populations, and no clinically significant differences were observed between them.¹⁴

In 2015, edaravone was approved in Japan and South Korea (as Radicut®) as a therapeutic option to slow down the progression of the disease in ALS subjects. This was followed by approval (as Radicava®) by the US FDA in 2017¹⁵, the Health Canada (as Radicava™) in 2018, and the Swissmedic and China in 2019.

